5. STATISTICAL ANALYSES

5.1. General Considerations

Descriptive statistics (i.e., N, mean, median, standard deviation (SD), interquartile (IQ) range, minimum, and maximum) will be used to summarize continuous variables. Counts and percentages will be used to summarize categorical variables. Graphical data displays (e.g., line plots) may also be used to summarize the data.

Analyses suitable for categorical data (e.g., chi-square tests, Cochran-Mantel-Haenszel tests, or logistic regression, as appropriate) will be used to compare the proportions of participants achieving selected endpoints (e.g., clinical response). In cases of rare events, Fisher's exact test will be used for treatment comparisons. Continuous response parameters measured at more than one postbaseline visit will be compared using Mixed-Effect Model Repeated Measure (MMRM) model (unless otherwise specified). If the normality assumption is in question, an appropriate transformation may be implemented before fitting MMRM model. Continuous response parameters measured at only one post-baseline visit will be compared using a stratified log-rank test or a log-rank test. The association between 2 categorical variables will be assessed based on a chi-square test and the association between a categorical variable and a continuous variable will be assessed based on a t-test.

A multiplicity-controlled testing procedure to control the Type-I error at a 2-sided 0.05 significance level over the primary and major secondary endpoints will be used (see Section 5.4.1.3.).

5.1.1. Visit Windows

Except for the early termination and unscheduled visits, actual scheduled visits will be used for over time summaries and listings with no visit windows applied.

5.1.2. Study Day and Relative Day

Study Day 1 refers to the day of the first study intervention administration of this Maintenance Study. All efficacy and safety assessments at all visits will be assigned a day relative to this day.

Study day for a visit is defined as:

- Visit date (date of Study Day 1) +1, if visit date is \geq date of Study Day 1
- Visit date date of Study Day 1, if visit date < date of Study Day 1

There is no 'Study Day 0'.

5.1.3. Induction Baseline Definition

The induction baseline is defined as the closest non-missing value on or prior to the induction reference start date.

5.1.4. Maintenance Baseline Definition

The maintenance baseline is defined as the closest non-missing value on or prior to the maintenance reference start date which is also post-induction baseline.

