Fecal calprotectin		X	X		X			X	X		At visits also requiring endoscopy, stool samples should be collected prior to the initiation of endoscopy bowel preparations. Refer to the At Home Stool Collection Manual for collection instructions.	
Pharmacokinetics/Immunogenicity												
Serum guselkumab concentration		X	X	X	X	X	X	X	X	X	
For all visits where study intervention will be administered, 1 blood sample should be collected prior to the start of study intervention administration for evaluation of serum concentrations and/or antibodies to study intervention. In addition, for IV infusion related visits, another blood draw should be taken approximately 60 minutes after the completion of the IV infusion for serum concentration measurement.
 
For visits where participants will receive both SC injection and IV infusion (Weeks I 12, I 16, and I 20), 1 blood sample for evaluation of serum concentrations and/or antibodies to study intervention should be collected first, followed by the IV infusion. Subcutaneous injection should follow 30 minutes after the completion of the IV infusion, and another blood draw should be taken approximately 60 minutes after the completion of the IV infusion for serum concentration measurement.
 
For clinical responders at the I 12 or I 24 visit, samples for evaluation of serum concentrations and antibodies should be collected at the time of study IP administration, M 0 timepoint, using the I 12/I 24 sample collection kit.
 
All reasonable attempts should be made to collect samples at the scheduled timepoints and record the actual dates and times of PK sample collections.
	
Antibodies to guselkumab		X	X	X	X			X	X	X		
Random guselkumab concentration (population PK sample)			X								One random blood sample for serum guselkumab concentration should be drawn at any time from the day following the Week I 0 study intervention administration to 1 day before the Week I 12 visit. This sample should not be drawn on or within 1 day of a scheduled visit during this time period (ie, Weeks I 0, I 4, I 8, and I 12). All reasonable attempts should be made to record the actual date and time of PK sample collection.	

Table 1: Screening and Week I-0 to Week I-24 of Induction Study 1 and Induction Study 2											
Phase	Screening	Treatment							Early Term ^{b,c}	Safety F/U ^{e,g}	Notes
Week	Within 8 weeks	I-0	I-4	I-8	I-12 ^{e,f}	I-16 ^e	I-20 ^e	I-24 ^{e,f}			
Study Procedures^{a,b,c,d}											

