
f. Only guselkumab clinical responders at Week I 12 and placebo crossover responders at Week I 24 will be rerandomized in the Maintenance Study. Guselkumab 24 Week responders and induction placebo responders at Week I 12 will enter the Maintenance study but will not be rerandomized.
 
g. All assessments are to be completed before study intervention administration, unless otherwise specified. It is recommended that PRO assessments be completed first.
 
h. For all assessments not marked at this visit, data from the study assessments performed at the Week I 12 visit (for participants in clinical response at Week I 12) or at the Week I 24 visit (for participants who were not in clinical response at Week I 12 but were in clinical response at Week I 24) will be used for the Week M 0 visit.
 
i. A participant who meets the criteria for clinical flare for the first time prior to Week M 32 should undergo an endoscopy (which need only be a flexible sigmoidoscopy) to determine loss of clinical response based on the modified Mayo score (Section 4.1.3.1).
 
j. If TB is suspected at any time during the study, a chest radiograph and QuantiFERON TB[®] (or T SPOT[®] for sites in Japan) test should be performed. In countries/territories where the QuantiFERON TB[®] test is not registered/approved, TB skin testing should also be performed (recommended but not required for study centers in Ukraine if tuberculin is not available).
 
k. Temperature, pulse/heart rate, respiratory rate, and blood pressure. At a study intervention administration visit, vital signs should be obtained before and approximately 30 minutes after SC injection, or if the participant reports any symptoms.
 
l. A urine pregnancy test must be performed before any study intervention administration for women of childbearing potential.
 
m. The C SSRS should be completed after all PROs and before any other tests, procedures, or other consultations to prevent influencing participant perceptions.
 
n. An injection site reaction is any adverse reaction at any SC study intervention injection site. Injection sites will be evaluated for reactions and any injection site reaction should be recorded as an adverse event.
 
o. Predose samples should be collected at all dosing visits before study intervention administration. All reasonable attempts should be made to collect samples at the scheduled time points and record the actual dates and times of sample collections.
 
p. Colonic biopsy samples will be collected from all participants during endoscopy for histologic assessment and RNA transcriptomic analysis. Pre defined sites will collect adjacent biopsy samples to support exploratory single cell isolation and analyses.
 
q. Whole blood samples will be collected for PBMC isolation from a subset of participants that provide biopsy samples for single cell analyses at selected sites. Whole blood (PBMC) samples should be collected within ±3 days of the endoscopy visit.
 
r. Serum biomarkers will be measured in all participants to evaluate the effects of study intervention on inflammatory proteins associated with UC, including cytokines associated with the IL 23 pathway.
 
s. Whole blood (RNA) will be measured in all participants to evaluate the molecular effects of study intervention in UC.
 
t. Fecal biomarkers may be used for evaluation of changes in inflammatory proteins or microbiome composition.
 
u. Participants who complete the safety and efficacy evaluations (including the required endoscopy procedure) at maintenance Week M 44 and who may benefit from continued study intervention, in the opinion of the investigator, will have the opportunity to participate in the LTE of the Maintenance Study.
 
v. At visits also requiring endoscopy, stool samples should be collected prior to the initiation of endoscopy bowel preparations. Refer to the At Home Stool Collection Manual for detailed instructions.
 
w. Should be completed if the Week M 0 visit is completed on a day other than that of the Week I 12 visit or Week I 24 visit.
 
x. Corticosteroid tapering must begin at M 0 for all participants receiving corticosteroids at baseline. Refer to Section 6.5.1 for guidance and requirements for corticosteroid use.
														

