3. OBJECTIVES AND ENDPOINTS

Definitions for Time Points and Endpoints

The analysis time points mentioned for each study or phase refer to Week 0 of that study or phase (induction or maintenance); for example, Week I-12 refers to Week 12 of induction (Study 1 or Study 2), or 12 weeks after Week 0 of these studies. Similarly, Week M-44 refers to 44 weeks after the first maintenance visit (Week M-0) of that study and *not* 44 weeks after the first induction visit.

A description of the Mayo score, the modified Mayo score, and the partial Mayo score is provided in Section 8.1.1. Refer to Section 8, Study Assessments and Procedures for evaluations related to endpoints.

Baseline definitions and efficacy endpoints definitions are as follows:

- **Induction baseline:** Week 0 of Induction Study 1 and Induction Study 2 (I-0 visit).
- **Maintenance baseline:** Week 0 of the Maintenance Study (M-0 visit).
- **Clinical remission:** A stool frequency subscore of 0 or 1, a rectal bleeding subscore of 0, and an endoscopy subscore of 0 or 1 with no friability present on the endoscopy, where the stool frequency subscore has not increased from induction baseline.
- **Clinical response:** A decrease from induction baseline in the modified Mayo score by $\geq 30\%$ and ≥ 2 points, with either a ≥ 1 -point decrease from baseline in the rectal bleeding subscore or a rectal bleeding subscore of 0 or 1.

Modified Mayo score: 3-component (stool frequency, rectal bleeding, and endoscopy subscores) Mayo score without the physician's global assessment.

- **Endoscopic healing:** An endoscopy subscore of 0 or 1 with no friability present on the endoscopy.
- **Endoscopic normalization:** An endoscopy subscore of 0.
- **Histologic healing:** Neutrophil infiltration in $<5\%$ of crypts, no crypt destruction, and no erosions, ulcerations or granulation tissue according to the Geboes grading system ([Geboes 2000](#)).
- **Histologic remission:** Absence of neutrophils from the mucosa (both lamina propria and epithelium), no crypt destruction, and no erosions, ulcerations or granulation tissue according to the Geboes grading system ([Geboes 2000](#)).
- **Histologic-endoscopic mucosal healing:** Achieving a combination of histologic healing and endoscopic healing, as defined above.
- **Histologic-endoscopic mucosal healing (Alternative definition):** Achieving a combination of histologic remission and endoscopic healing, as defined above.

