- Clinical response, clinical remission, endoscopic healing, endoscopic normalization, histologic-endoscopic mucosal healing, histologic-endoscopic mucosal healing (Alternative definition), and deep histologic-endoscopic mucosal healing at Week I-12 based on the local endoscopy subscores.
- Clinical response, clinical remission, symptomatic remission, endoscopic healing, endoscopic normalization, histologic healing, histologic remission, histologic-endoscopic mucosal healing, histologic-endoscopic mucosal healing (Alternative definition), and deep histologic-endoscopic mucosal healing at Week I-12 by ADT-Failure status and biologic-failure status (eg, biologic-naïve, biologic-failure, biologic non-failure, and biologic-experienced without documented failure [ie, discontinued biologic therapy for other reasons]), to be defined in the SAP).

- Clinical response, clinical remission, symptomatic remission, endoscopic healing, endoscopic normalization, histologic healing, histologic remission, histologic-endoscopic mucosal healing, histologic-endoscopic mucosal healing (Alternative definition), and deep histologic-endoscopic mucosal healing at Week I-12 by the colonic molecular prediction signature status at baseline.
- Change from baseline in the UCEIS score at Week I-12.
- UCEIS score ≤ 4 at Week I-12.
- Extraintestinal manifestations at Week I-12.

CRP and Fecal Calprotectin

- Change from baseline in CRP at Weeks I-4, I-8, and I-12.
- Change from baseline in CRP at Weeks I-4, I-8, and I-12 among participants with abnormal CRP at baseline.
- Change from baseline in fecal calprotectin at Weeks I-4 and I-12.
- Change from baseline in fecal calprotectin at Weeks I-4 and I-12 among participants with abnormal fecal calprotectin at baseline.
- Normalization of CRP at Weeks I-4, I-8, and I-12 among participants with abnormal CRP at baseline.
- Normalization of fecal calprotectin at Weeks I-4 and I-12 among participants with abnormal fecal calprotectin at baseline.

Patient-Reported Outcomes

- Change from baseline in the total score of the IBDQ at Week I-12.
- A ≥ 16 or >20 -point improvement from baseline in the IBDQ total score at Week I-12.
- Change from baseline in each of the 4 dimensions of the IBDQ at Week I-12.
- Change from baseline in the domains T-scores of PROMIS-29 and the pain intensity at Week I-12.
- Clinically meaningful improvement (to be defined in the SAP) in the domains T-scores of PROMIS-29 and the pain intensity at Week I-12.

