5.9.3. Additional Safety Assessments

5.9.3.1. Clinical Laboratory Tests

Laboratory assessments include, but are not limited to, the assessments listed below:

• Hematology: hemoglobin, hematocrit, platelet count, total and differential WBC count.

• Blood chemistry: total and direct bilirubin, alanine aminotransferase (ALT), aspartate aminotransferase (AST), alkaline phosphatase, albumin, total protein, calcium, phosphate, sodium, potassium, chloride, blood urea nitrogen (BUN), and creatinine.

The maintenance baseline value for a participant is the value closest to but prior to the first dose of study agent of the maintenance study unless specified otherwise. In addition, change from maintenance baseline is defined to be the assessment at the post-maintenance baseline visit minus the assessment at maintenance baseline. There will be no imputation for missing laboratory values.

Laboratory parameters and change from maintenance baseline in laboratory parameters (hematology and chemistry) through Week M-44 will be summarized and displayed by treatment group based on the **Randomized Safety Analysis Set** and **the Nonrandomized Safety Analysis Set**.

The following summaries will also be presented through Week M-44 for the **Randomized Safety Analysis Set**, the **Nonrandomized Safety Analysis Set**, and the **Safety Analysis Set**:

- Summary of maximum modified National Cancer Institute Common Terminology Criteria for Adverse Events (NCI-CTCAE) toxicity grade for post-maintenance baseline laboratory values through Week M-44 for the predefined hematology and chemistry lab parameters except for liver tests (i.e., ALT, AST, alkaline phosphatase, and total bilirubin). This summary will also be presented for the **All Treated Analysis Set**. Shift tables for maximum modified NCI-CTCAE toxicity grade from maintenance baseline through Week M-44 will be summarized for the predefined hematology and chemistry lab parameters except for liver tests (i.e., ALT, AST, alkaline phosphatase, and total bilirubin).
- Summary of maximum post-maintenance baseline measurement through Week M-44 for liver tests (i.e., ALT, AST, alkaline phosphatase, and total bilirubin) relative to ULN threshold. This summary will also be presented for the All Treated Analysis Set, the Safety All Randomized, the Treated Analysis Set, and the Safety All Nonrandomized and Treated Analysis Set.

Line graphs will also be provided for ALT, AST, total bilirubin, and alkaline phosphatase.

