Refractory, dependent, or intolerant to oral or IV corticosteroids, but not refractory or intolerant to 6-MP/AZA	yesno
Refractory, dependent or intolerant to oral or IV corticosteroids, and refractory or intolerant to 6-MP/AZA	yesno
	sease characteristics at Week M-0
Endoscopic healing status	 yes no
CRP	 ≤ 3 mg/L > 3 mg/L ≤ median > median
Fecal calprotectin	 ≤ 250 mg/kg > 250 mg/kg
IBDQ remission	• yes • no
Fatigue response	yesno
Induction treatment	 guselkumab 400 mg IV guselkumab 200 mg IV placebo crossover to guselkumab 200 mg IV

In addition, the consistency of treatment effect for the primary and major secondary endpoints, histologic healing, histologic remission, histologic-endoscopic mucosal healing (Alternative definition 1-2), and deep histologic-endoscopic mucosal healing, will be evaluated for the following subgroups in a table summary:

Subgroup	Definition	
Induction baseline body weight	 ≤ 1st quartile > 1st quartile and ≤ 2nd quartile > 2nd quartile and ≤ 3rd quartile > 3rd quartile 	

Subgroup	Definition
CRP (at Week 0 of the induction study and the maintenance study)	• ≤ 3 mg/L • ≥ 3 mg/L • ≤ median • > median
Fecal calprotectin (at Week 0 of the induction study and the maintenance study)	 ≤ 250 mg/kg > 250 mg/kg
Fecal calprotectin (at Week 0 of the induction study and the maintenance study)	 ≤ 1st quartile > 1st quartile and ≤ 2nd quartile > 2nd quartile and ≤ 3rd quartile > 3rd quartile
ADT failure profile	 ADT-naïve ADT-experienced but not failed ADT-non failure ADT-Failure
Biologic failure profile	 Biologic-naïve Biologic-experienced without documented failure [i.e., discontinued biologic therapy for other reasons] Biologic-non failure Biologic-failure
Colonic molecular predictive signature (MPS) status at induction baseline	Predicted endoscopic healingPredicted endoscopic non-healing
Induction treatment	 guselkumab 400 mg IV guselkumab 200 mg IV placebo crossover to guselkumab 200 mg IV

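### SAP 5.1.4 lets a Week I-12 value taken before any guselkumab stand as maintenance baseline for a placebo-crossover responder with no Week I-24 value

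*SAP*

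**What the plan says.** SAP 5.1.4 defines maintenance baseline as the "closest non-missing value on or prior to the maintenance reference start date which is also post-induction baseline". SAP 5.1.3 supplies the lower limit: "The induction baseline is defined as the closest non-missing value on or prior to the induction reference start date". SAP 5.1.1 applies no visit windows to scheduled visits, so nothing else limits how far back the rule can look. The SAP does not define the maintenance reference start date.

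The protocol is narrower. Section 3 defines maintenance baseline as "Week 0 of the Maintenance Study (M-0 visit"). Table 2 footnote h says where unmarked M-0 assessments come from: the Week I-12 visit for Week I-12 responders, and, for the others, the data obtained "at the Week I 24 visit (for participants who were not in clinical response at Week I 12 but were in clinical response at Week", where the sentence goes on to name I-24.

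SAP Appendix 2 reports no change to protocol-planned analyses. The Amendment 2 table of changes gives clarification as the reason for adding the baseline definitions.

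**The concern.** Placebo-crossover responders receive placebo to Week I-12, do not respond, receive guselkumab IV at Weeks I-12, I-16 and I-20, and enter maintenance after responding at Week I-24. Their maintenance baseline should describe the state reached after guselkumab induction. A Week I-12 value describes the state before it.

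For such a participant, part of any fall in calprotectin shown as change from maintenance baseline would really be the induction effect. The same value would serve as the baseline covariate and would decide the Week M-0 calprotectin stratum. A placebo-period IBDQ or fatigue score would decide whether the participant counts as in IBDQ remission or fatigue response at maintenance entry, and so who enters the denominators for maintaining those states.

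**Working it through.** **1. When values exist** (protocol Tables 1 and 2)

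| Measure | Scheduled in induction | At M-0 |
|---|---|---|
| Fecal calprotectin | I-0, I-4, I-12, I-24 | none |
| IBDQ, PROMIS-29, PROMIS Fatigue 7a | I-0, I-12, I-24 | none |
| CRP | every visit from I-0 to I-24 | none |

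**2. Is the Week I-12 value before guselkumab?** Yes. Table 1 footnote d puts assessments before dosing. For stool, the table adds: "At visits also requiring endoscopy, stool samples should be collected prior to the initiation of endoscopy bowel preparations". The first guselkumab infusion for crossover participants is given at Week I-12 (protocol 6.1.1.2 and 6.1.2).

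**3. What the qualifier means.** Induction baseline is defined immediately above, as the value on or before induction start. SAP 5.9.3.1 uses the parallel phrase in the same sense: "change from maintenance baseline is defined to be the assessment at the post-maintenance baseline visit minus the assessment at maintenance baseline". So values at I-4, I-12 and I-24 all qualify. Reading the phrase as meaning after the induction period is unlikely.

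**4. The rule applied to calprotectin in a crossover responder**

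| Missing | SAP 5.1.4 gives | Footnote h source visit gives |
|---|---|---|
| nothing | I-24 | I-24 |
| I-24 | I-12, before guselkumab | no value |
| I-24 and I-12 | I-4, on placebo | no value |

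For IBDQ and PROMIS, a missing I-24 value also returns I-12. CRP is less exposed: a missing I-24 value returns I-20, after two guselkumab infusions.

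The two randomized groups are treated differently. A guselkumab Week I-12 responder with no Week I-12 IBDQ or PROMIS value has no earlier qualifying value, so the baseline is missing. A crossover responder with no Week I-24 value gets a pre-guselkumab one.

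**5. Size of the group.** SAP Table 2, Group B = placebo participants × share crossing over × response rate.

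- 354 × 0.60 × 0.60 = 127.4, against the stated 127. At response rates of 50%, 55% and 65% the formula gives 106.2, 116.8 and 138.1, against 106, 117 and 138, so the plan's figures reproduce.
- Share of the primary population: 127 / 484 = 26.2%.

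**6. Number affected.** The documents give no rate of missing Week I-24 samples. Assuming 5%, 10% and 15%, and that the Week I-12 sample exists:

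- 127 × 0.05 = 6.4, or 1.3% of 484
- 127 × 0.10 = 12.7, or 2.6% of 484
- 127 × 0.15 = 19.1, or 3.9% of 484

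Over three equal arms that is about 2 to 6 per arm. The rates for IBDQ and PROMIS are separate and also unknown.

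**7. Where the value is used**

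- Change and percentage change from maintenance baseline, and the baseline term in the repeated-measures model (SAP 5.5 and 5.5.3).
- Week M-0 subgroups in SAP 5.10.6: calprotectin, IBDQ remission and fatigue response for the primary endpoint, and "Fecal calprotectin (at Week 0 of the induction study and the maintenance study"), by cut-off and quartile, for the primary and major secondary endpoints.
- Denominators for maintenance of IBDQ remission, of IBDQ improvement and of fatigue response (SAP 5.5).
- Week M-0 calprotectin and IBDQ remission in the characteristics table (SAP Appendix 3).

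**The case against.** The strongest reply is that nothing confirmatory depends on this, and that stands. Clinical remission, symptomatic remission, clinical response and fatigue response refer to induction baseline where they use a baseline at all. IBDQ remission and the endoscopic and histologic endpoints are absolute states at Week M-44. Remission status at maintenance baseline does enter the stratified test and one major secondary subset, but it uses Mayo components that entry at Week I-12 or I-24 already requires.

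A reader might infer bias between arms. The documents do not support that. Randomization is stratified by induction treatment, with placebo crossover as its own level, and the Week I-24 sample precedes any maintenance dose. The wrong values should fall about evenly across the arms. Calprotectin change from induction baseline is also planned and does not use 5.1.4.

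A reader might also put the affected share at up to 15% of the population. That adds guselkumab responders given a Week I-4 value: 357 × 0.15 ≈ 54, and (19 + 54) / 484 = 15%. Those values are stale, but they follow a guselkumab dose, so this is a different and lesser fault. The 15% is simply the assumed rate restated.

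Nor is an effect on the histology associations established. SAP 5.5 refers there to healing at Week M-0, and the binary rule in SAP 5.5.3 already counts missing data as not achieved.

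Finally, footnote h names a source visit and is silent on a missing value, and the protocol leaves analysis detail to the SAP. With complete data the documents agree. That softens the conflict but does not remove it: the protocol offers no earlier source for M-0 data, and the SAP declares no departure.

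**Conclusion.** The point holds as a fault in a stated rule. When a crossover responder's Week I-24 calprotectin, IBDQ or PROMIS value is missing, SAP 5.1.4 labels a pre-guselkumab value as maintenance baseline.

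The consequences are distorted within-arm change in endpoints with nominal p-values, a wrong baseline covariate, misassigned Week M-0 subgroups and conditional denominators, and some wrong entries in the Week M-0 table. The estimate of 6 to 19 participants rests on an assumed 5-15% missing rate, the planned 60% response rate and 60% crossover share, and the Week I-12 sample being present. The point does not call the primary or major secondary tests into question. It is worth correcting because the correction is simple.

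**What to change.** Restrict SAP 5.1.4 to the last non-missing value from the qualifying visit (Week I-12 for Week I-12 responders, Week I-24 for Week I-24 responders) through the first maintenance dose. State that a value taken before the first guselkumab dose is never used for a crossover responder. Otherwise set maintenance baseline to missing. Define the maintenance reference start date.

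Also state how a missing maintenance baseline is handled, because the SAP has no rule for it: the repeated-measures model does not impute, and the multiple imputation for ANCOVA takes the baseline value as an input. Workable choices are to omit the participant from change-from-maintenance-baseline models, or to impute the baseline by multiple imputation under missing at random. In either case, show a missing level in the subgroup and baseline tables.

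The cost is a short SAP edit and one derivation change. The downside is some missing maintenance baselines in exploratory analyses. Under the same assumed rates, these would include about 18 to 54 of the 357 guselkumab responders (357 × 0.05 to 357 × 0.15), who now get a Week I-4 calprotectin value.
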